13.3 Patients will be notified by research staff if they will be partially withdrawn from the research, as reviewed in their study letter (Appendix X) as well.

14 Risks to Subjects*

- 14.1 There are risks to taking part in any research study. The primary risk of this study is loss of privacy or confidentiality. The risk of loss of privacy or confidentiality by using the STAMP+CBT app or taking part in this study is minimal. The study team has taken many steps to prevent any loss of privacy or confidentiality, including training of all clinic and research staff in best practices, rules, and regulations surrounding privacy and confidentiality, collecting research data using unique study ID numbers instead of names or other identifying information, and use of data collection systems that meet data security standards.
- 14.2 Recruitment and Informed Consent: Participants will only be approached if approval is received by their treating clinician. If the physician deems them unsuitable for the study, they will not be approached. Participants will be approached in clinic or by phone by the RA in a private and confidential manner. If the patient is eligible and interested in participation, the study letter and consent forms (Appendices X and AD) will be reviewed with the participant.

In the case of remote approach by phone, the RA will attempt to contact the patient 3 times. If the patient contact cannot be established, the RA will email a copy of the recruitment letter to the patient (Appendix AC). The recruitment letter encourages the patient to reach out to the study staff if they are interested in participating. If a patient reaches out to the study staff then the study letter and consent form will be reviewed before the patient provides written consent. During remote approaches by phone the study letter and consent forms will be sent by email through a secure and personalized link in the FDA and HSSH compliant Mass General Brigham/Partners REDCap database. While discussing the study letter and consent the study staff will emphasize that participation is voluntary and the participant may stop participating at any time. Consent discussions may take place over the phone or HIPAA compliant Zoom.

The study letter and consent forms for consent to participate will adhere to strict standards regarding its content. Required sections include: Introduction; Why is this research study being done? What

other options are there? What is involved in the research study? How long will I be in this research study? What are the risks or discomforts of the research study? What are the benefits of the research study? Can I stop being in the research study and what are my rights? What are the costs? What happens if I am injured or sick because I took part in this research study? What about confidentiality? Whom do I contact if I have questions about the research study?

15 Potential Benefits to Subjects*

15.1 Using the STAMP+CBT app and taking part in this research study may or may not benefit participants. We hope that by reviewing the content in the STAMP+CBT app, patients are able to learn to better manage their symptoms and the increased flow of information between a patient and their care team improves their experiences. We also hope the information learned from this research study will provide more information about how to best help patients and their care team work together during and between visits to achieve better symptom management in cancer patients.

16 Vulnerable Populations*

16.1 This research does not involve vulnerable populations of prisoners, children, cognitively impaired adults, or pregnant women. Prisoners, children, cognitively impaired adults, and pregnant women are excluded.

17 Community-Based Participatory Research*

N/A

18 Setting

18.1 This is a pilot study that will take place at the Dana-Farber Cancer Institute. The research procedures will all be conducted online through secure, HIPAA compliant portals (i.e. Zoom, partners email, etc.). The research team will identify and recruit potential subjects through outpatient palliative care, GCC, and satellite clinics including MV and LD. See section 22.0.

19 Resources Available

- 19.1 The research team is well-qualified to perform their duties. [name] has extensive experience in conducting research studies in cancer distress screening, pain psychology, and education. She has deep knowledge of the clinical and research environments and the patient population and culture at DFCI.
- *19.2* This study team will be taking place under the Department of Psychosocial Oncology and Palliative Care (POPC) at Dana-Farber.

The POPC Department maintains its own server infrastructure and systems administration staff that provide data storage, data backup, and data security in support of large data analysis projects. The servers are configured as a virtual server pool with virtual server hosts connected to a centralized Storage Area Network (SAN) device. Server virtualization increases the efficiency and flexibility of the server pool while minimizing downtime and cost. The server pool currently has 20 processor cores and a data storage capacity of 9 terabytes. This server infrastructure has a dedicated Systems Administrator to optimize performance, maintain security patches, perform backups, and execute other related tasks. Researchers in the Division have access to additional resources through the Research Computing group. Research Computing provides a variety of services including file server space, backup services, website hosting, and support of some workstation computers.

All individuals in the study team will review the protocol and be updated on protocol procedures and study needs, at the beginning of study activation and throughout the study period.

20 Prior Approvals

- 20.1 The existing pain educational text and audio-visual content has been previously approved in the initial STAMP pilot study (DF/HCC IRB #18-504 and # 384-811).
- 20.2 The additional pain CBT content was developed during study procedures previously approved in DF/HCC IRB #20-453. This content can be viewed in appendices C, D, U, Y, and Z.

21 Recruitment Methods

- 21.1 Identifying potential subjects: Potentially eligible patients will be identified by 1) referrals from clinic staff, and 2) by screening the EMR for outpatient solid tumor or hematology disease center clinic schedules, 3) by screening the palliative care clinic schedules. Once the study team identifies a potentially eligible patient, the team will reach out to the treating clinician for permission to approach and offer engagement in the study. If the provider does not approve that the study staff approach a patient, the study staff with NOT approach the patient to offer engagement in the study. Patients will provide written consent on the consent form after viewing study letter according to IRB procedures (see Appendices X and AD).
- 21.2 Recruitment of potential subjects: Under a HIPAA waiver, study staff will look in the electronic medical record, scheduling systems, and inpatient lists to identify potentially eligible patients who meet the eligibility criteria. Study staff may also query Epic, administrative/ operations/billing databases, order entry databases,

and/or cancer registry databases to identify potentially eligible participants. Study staff may also accept potential patient referrals from site clinicians, through palliative care, DFCI satellite clinics Merrimack Valley and Londonderry, and outpatient GCC clinic. Purposive sampling based on data from the electronic medical record (e.g., demographics, cancer stage, number of recent hospitalizations, number of prescription drugs) will be used to ensure that perspectives of diverse patients are included.

- 21.3 Patient approaches can occur through the following mechanisms dependent upon COVID-19 related research regulations and clinic operations at the time.
 - In person approach: A research assistant (RA) will approach the patient in clinic to explain the study and offer participation. Interested participants will then review the study letter and consent form with a research team member (Appendices X and AD) and if interested provide written consent. The patient and RA will then set up a time for onboarding to the application.
 - Remote approach: The clinician can introduce the study to the patient during a clinic visit and the RA will follow up by phone to explain the study and offer participation. The study letter and consent form will be sent electronically through a secure and personalized link in REDCap (Appendices X and AD). The RA will attempt to contact the patient three times. If no contact is established, the RA will email the participant a copy of the recruitment letter (Appendix AC). The recruitment letter introduces the study and encourages the patient to contact the study team if they are interested in participating. If the patient contacts the RA after the recruitment letter, the RA will review the study letter and consent form before obtaining written consent.
- 21.4 See study letter Appendix X, recruitment letter Appendix AC, and consent form Appendix AD for the Pilot Cohort.
- 21.5 A \$25 giftcard will be provided upon completion of the 4-week intervention period, and another \$25 gift card will be provided when patients complete the 2week post intervention period survey. Clinicians will not receive compensation for their engagement.

22 Local Number of Subjects

22.1 This project will ONLY be taking place at Dana-Farber and participating DFCI satellite clinics. Therefore, all study participants will be recruited on site and through remote approach and follow-up

(phone and zoom). In total, approximately 15 subjects will be accrued at DFCI and participating DFCI satellite clinics.

Activity	Maximum # of participants
Pilot Cohort	Up to 15

23 Provisions to Protect the Privacy Interests of Subjects

23.1 To protect PHI, the following measures will be taken. Patients will be approached and interviewed in private settings. All study form hard copies will use only de-identified unique study ID numbers and be kept in the patients' study files in locked drawers to which only the designated study team member has a key. All electronic data will be kept on secure, password protected servers as evaluated and managed by the Dana-Farber Department of Research Computing and IS.

Departmental and institute-wide policies enforce the protection of our electronic information, especially with regards to HIPAA regulations and the integrity of patient care. These policies also safeguard again theft, abuse, misuse, and any form of damage. The scope of protection includes information which is printed from or stored on a database, mainframe, server desktop, laptop, PDA, CD-ROM, hard disk, flash drive, optical platter, tape, smart phone, network, telephone, and other computer-enabled medical devices. These policies regulate usage of system IDs, passwords, e-mail accounts, anti-virus mechanisms, encryption, mobile devices, remote access, remote control software, and wireless devices. IS responsibilities and governance including firewall protection of all Dana-Farber internal networks and the internet, system evaluation, risk analysis, information access, regular review of user accounts, systems audit, regular review of remote access, and physical location access. Specific to this project, no data will be stored on laptops at any point and secure transfer protocols will be used for any electronic exchange of information. All staff/users receive mandatory institutional trainings on Information Security and must adhere to policies at all times.

Subjects will be approached for potential participation in private or by phone. They will also complete all study assessments in private and at their own comfort (remote completion). At each assessment, subjects will be reminded that they can skip any questions they do not wish to answer and are free to withdraw from the study at any time.

Study research assistants will have access to subject's medical records to abstract information as discussed in other sections of this protocol. RAs will only access information that is necessary to collect for the study protocol and will not be permitted to access the medical record for other purposes.

24 Compensation for Research-Related Injury

N/A

25 Economic Burden to Subjects

25.1 Costs that subjects may be responsible for because of participation in the research: Subjects participating in this study will be asked to complete online surveys using an internet-enabled device. Participants will have to use their own hardware (e.g., smartphone, tablet, computer) and their own WiFi or Data Plan which may cost them money; subjects are responsible for these costs. Devices and/or data plans may also be provided by the study staff to interested participants who do not own an android device.

Patient participants in the Pilot Cohort will receive a \$25 gift card upon completion of the 4-week intervention period, and a second \$25 gift card upon completion of the 2-week post-intervention survey.

26 Consent Process

26.1 Potentially eligible patients will be identified by 1) referrals from clinic staff, or 2) by screening the EMR for outpatient GCC or palliative care clinic schedules. Once the study team identifies a potentially eligible patient, the team will reach out to the treating clinician for permission to approach.

Once approved to approach, the study staff may approach patients in-person during clinic. Once approached the RA will review the study letter and consent form with the patient (Appendices X and AD). If it is not possible for the RA to meet the patient during a clinic visit, the clinician may introduce the study and the RA will follow up by phone. During a phone call the RA will explain the study and offer participation before obtaining written informed consent. During this phone call, the RA will email a copy of the study letter and consent form and the participant will provide written consent. The RA will send the study letter and consent forms through a secure and personalized link in the FDA and HSSH compliant Mass General Brigham/Partners REDCap database. The RA will attempt to contact a patient three times. If contact is not established, the RA will email a copy of the recruitment letter to introduce the study (Appendix AC). The letter encourages the patient to contact the research team if they are interested in participating in the study. If the patient then contacts the research team, the study letter and consent form will be reviewed remotely during a phone call with the patient before obtaining written consent. If the RA is

unable to establish contact with the patient after 3 call contacts and if the patients does not respond to the email recruitment letter, the patients will no longer be contacted

All interested participants will provide written consent after thorough review of the study letter and consent form. Next, they will complete the baseline survey to ensure enrollment in the study. Thereafter, the RA will coordinate with the patient to onboard with the pilot application. They will be notified that participation is completely voluntary and can be stopped at any time for any reason.

27 Process to Document Consent in Writing

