An RA will ask the patient to complete a baseline survey assessment after consenting, at the end of the 4-week intervention study period, and at the end of the 2-week post intervention period to assess key outcomes (pain severity/interference,⁴² QOL⁴³), potential mediators of intervention effects (catastrophizing⁴⁴, self-efficacy⁴⁵, perceived stress⁴⁶, anxiety/depression⁴⁷, sleep⁴⁸), acceptability,⁴⁹ and usability⁵⁰. The survey can be completed remotely though a link to a Partners Healthcare compliant electronic survey system (e.g. REDCap), over the phone with the RA, over Zoom with the RA,

in person with pen and paper or on a tablet. The Baseline survey will assess socio-demographics, barriers to pain management, pain severity, opioid use, pain and psychological symptoms, and quality of life, with metrics shown in Table 5. End of 4-week intervention period survey will largely replicate the baseline survey; additionally, patients will rate their satisfaction with STAMP+CBT using the 6-item Acceptability E-scale. Surveys will be used to assess pain and psychological symptom trajectory, medication use, and quality of life. See **Appendix P** for the Baseline survey items, **Appendix Q** for 4-week (end of 4-week intervention period) survey items, and **Appendix R** for 2-week (post intervention period) follow-up survey items. Additionally, a subset of patients (up to 10) will be invited for a qualitative interview focused on study burden, facilitators/barriers to app use, satisfaction, and perceived utility in order to guide future refinements to the app (see Appendix T) when they complete use of the app at 4 weeks (end of intervention study period).

Intervention

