and pain specific CBT concepts (Appendices C, D, and F). Content will be delivered on a schedule to ensure that patients receive all pain CBT and medication education available (Appendix U). STAMP+CBT prompts patients to take daily surveys for reporting of pain, pain catastrophizing, mood, opioid/pain medication use, and sleep symptoms and progress towards individualized goals (Appendix U). At the end of each survey, patients receive feedback according to their symptom severity, with links to tailored educational content about pain and psychological symptom management. (Appendix U). Patients also complete weekly surveys for reporting symptoms listed above as well as goal progress. If patients report any severe symptoms, they are instructed to contact their care team immediately, with a telephone number included on the application screen, see table 2, or to go the Emergency room/call 911 for a true medical emergency. If patients' pain is poorly controlled but not severe enough to be prompted to immediately contact their care team (for example if their average pain is above a 4 and not acceptable), they are reminded to contact their care teams if their symptoms worsen or they are concerned about it.

One protocol-mandated study staff outreach to patients will occur within a week of enrollment. An RA will call to assess any technical or usability problems with the app (e.g. how to access the app on their phone, where to find certain study areas, etc.). These technical discussions will be optional for the patient and more can be scheduled if requested. Thereafter, the RA will monitor the STAMP+CBT dashboard twice daily (Mon-Fri), for any patient reported severe symptoms (Table 2). If a patient reports one of these severe symptoms, the RA will contact the patient's nurse through a secure EPIC message to notify the patient's care team. Additionally, to assist in population management, a *tiered system notifications*, in the portal will indicate symptom severity, need for outreach and/or management changes (See Table 3). As an additional safety measure, the application always prompts the patients to contact their care team for any severe symptoms they report and there is no expectation for proactive clinician outreach. These procedures have been approved by participating clinic nurses. The application provides a direct link to call the Outpatient Palliative Care Clinic at DFCI.

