9.4 MONITOR SUBJECTS FOR SAFETY AND MINIMIZE

RISKS: The risks to participants in the Pilot Cohort are minimal. The primary risk is loss of confidentiality/privacy. To monitor the risk of loss of confidentiality/privacy, the study team has ensured that the STAMP+CBT app is HIPAA compliant and meets the privacy and security standards set by DF/HCC, and will continue to do so with modifications in this study (IT approval received from [name]). In addition, all collected study data will be maintained in a secure location and personal identifiers will be removed. As described above, end of study interviews will be audio and video recorded, and transcribed for analysis of participant feedback. For the patients engaging in qualitative interviews, their video recorded data will be destroyed after manuscript publication.

Risks to participants in the Pilot Cohort

- Physical risks: Physical risks to subjects include if they feel reassured by the app's feedback/content and choose not to contact their care team for severe symptoms. It is also theoretically possible that patients are given medication advice that is either ineffective at relieving pain.
- Psychological risks: Reporting pain and psychological symptoms daily may be distressing for some patients. It may also be the case that reviewing psychological content may be distressing as awareness of cognitive and emotional factors relevant to pain will be acknowledged.

• Privacy risks: There is a risk of privacy violation or loss of confidentiality; however, this is anticipated to be minimal, and the study team is committed to guaranteeing adequate protection against risk as described in the following section.

9.5 Data to be collected:

- 9.5.1 Interview Data: Audio and video recordings of feedback will be collected from all interview participants regarding their perceived feasibility and acceptability of the mobile application as well as their experience with the app.
- 9.5.2 E-Acceptability (Survey) Data: Participants will complete an acceptability survey following review of finalized content (see Appendices I).
- 9.5.3 Chart Abstraction: Baseline demographic and clinical data will be collected from all patient participants via chart abstraction. Data will also be collected at the end of the pilot intervention. Data will include non-identifiable clinical/demographic information, including the following:
 - 9.5.3.1 Gender
 - 9.5.3.2 Age
 - 9.5.3.3 Ethnicity
 - 9.5.3.4 Race

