 - 9.5.3.5 Cancer type
 - 9.5.3.6 Cancer stage
 - 9.5.3.7 Opioid medications
 - 9.5.3.8 Pain score during last visit (see Appendices O).
 - 9.5.3.9 Health service utilization (e.g. ED visits, hospitalizations, unplanned urgent clinic visits, changes to opioid medications, psychosocial oncology visits)
 - 9.5.4 Survey Assessment Data: Demographic, disease, medication, pain, mood, stress, and sleep data will be collected at baseline before the intervention, end of the 4week intervention, and at the end of the 2-week post intervention period (see Appendices P, Q, R). T1 and T2 of Table 5.
 - 9.5.5 Symptom Reporting: Individual pain, pain interference, pain medication use, stress, mood, and sleep symptoms as well as pain management data will be recorded for each participant over the course of the pilot intervention (Appendix U). Participants will report their symptoms and management daily and weekly.
- *9.6* **Long term follow-up:** Participants in the Pilot Cohort complete a survey assessment assessing quality of life, pain, psychological

measures, healthcare utilization, and app use at the end of the 2 weeks post-intervention (T3 of Table 5).

Measures collected via patient assessments			Survey		App data	Chart review
Assessment	Measure	T1	T2	T3		
Socio-demographics	Standard	Х				
Clinical characteristics	Standard					Х
Baseline cellphone use	MTUAS	х				
Pain	BPI	х	Х	х		
severity/interference						
Opioid use/adherence	Self-report	Х	х	Х		
Quality of life	FACT-G	Х	Х	Х		
Satisfaction	Novel metric		Х			
Use of STAMP+CBT	-		Х	Х	Х	
Usability	SUS		Х			
Management changes	-					Х
Healthcare utilization	-		Х	Х	Х	Х
Self-efficacy in	PROMIS	Х	Х			
managing symptoms						
Self-efficacy in	PROMIS	Х	Х			
managing medications						
Pain catastrophizing	PCS	Х	Х	Х		
Stress	PSS	Х	Х	Х		
Patient reported	PRO-	Х	х	Х		
outcomes	CTCAE					
Depression and	PROMIS	Х	х	х		
Anxiety						
Sleep Disturbance	PROMIS	X	X	Х		

Table 5: Measures collected from patients at each of three survey timepoints

10 Data and Specimen Banking*

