- 11.2 Statistical analyses will be utilized in the pilot intervention portion of this study to ascertain feasibility and acceptability. We will measure time spent on the app per day and per week, completion rates for surveys and content review, and frequency of log-ons over the course of the pilot. The primary objective is to determine feasibility and acceptability of STAMP+CBT. Defined using precision analysis, we will consider the intervention to be feasible if >70% of subjects complete \geq 4 of the 6 pain-CBT modules and patients will complete 50% of surveys by the end of 4-weeks (completion of the 4-week intervention study period and completion of the 2-week post intervention period).^{40,41} A module will be considered complete if the participant engages in >70% of its content, including completing mHealth survey items, psycho-educational content, and app exercises. The intervention will be considered acceptable if >80% of the acceptability items are rated 4 or higher/5; lower ratings will lead to app refinements. Other feasibility measures will assess time to accrual, participation rates, and study retention and completion rates. Power calculation: With 10 patients, we will be able to estimate these proportions with margins of error (half of a 95% confidence

interval) of approximately 18% or less assuming that the feasibility threshold of 70% is reached. This margin of error is small enough so that proportion estimates relevant to study feasibility will be accurate and provide informative guidance for future, larger studies. Although power is not sufficient in this pilot, we will explore associations between levels of engagement and changes in pain severity/interference, opioid use, catastrophizing, sleep, mood, and pain self-efficacy.

- 11.3 The data the research team will access regarding app utilization will include; date and time of app log-ins, date of time of survey completion, survey responses, including clinical reporting of daily symptoms and medication usage, total app log-ins during intervention period, percent of surveys completed during intervention period, date time and frequency patients access external educational content.
- 11.4 PHI data will be collected using REDCap and the STAMP+CBT app.

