As such, the only adverse event that will be monitored and reported is psychological distress as determined by the treating oncologist or palliative care provider. For any patient who exhibits severe distress as result of the study procedures, the study research assistant will notify the patients' oncologist, palliative care provider, and/or social worker for appropriate response, including possible mental health referral if necessary. Furthermore, participants will be *reminded that participation is voluntary and can be stopped at any time for any reason. See the DSMP* (*Appendix N*) for more details.

12.1 Protection against physical risks: The study team has placed extensive protections against the aforementioned physical risks of the app. These protections significantly exceed the level of support and guidance that patients would receive with usual care. Moreover, patients' symptom reports will be reviewed daily by the study staff and shared with clinical nurse navigators that are part of the patients' care teams, which represents closer monitoring than usual care. Finally, the patient-facing app always instructs patients to contact their care teams and reminds them that the portal is not monitored continuously, or to call 911/go to an emergency room for medical emergencies. First, the application sets a low bar for instructing patients to contact their care teams for reported symptoms. This includes reporting any new pain, fever, new or worsening back pain, new or worsening chest pain, any pain rated > 8 out of a 0 to 10 scale (See table 2 for the detailed list). Moreover, if patients report moderate to severe pain levels that do not meet the previous criteria, in addition to receiving education about their pain management, they are also reminded that their care team wants to hear from them if they are concerned about their symptoms or if their symptoms are not improving. A link to their care team's number is included in the application. This level of support is much greater than what patients have usually with routine care.

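### Distress is reported as an adverse event only when the treating clinician determines it, and no planned summary counts patients who deteriorate on the distress scales the study already collects.

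*Combined protocol and SAP*

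**What the plan says.** Section 9.4 (psychological risks) accepts that the intervention may itself cause distress: "Reporting pain and psychological symptoms daily may be distressing for some patients". It says the same of reviewing the psychological content.

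Section 12 then limits adverse event reporting: "the only adverse event that will be monitored and reported is psychological distress as determined by the treating oncologist or palliative care provider". It adds an escalation step, "For any patient who exhibits severe distress as result of the study procedures, the study research assistant will notify" the care team, and refers to Appendix N for more detail. The text gives no instrument, cut-off, grade, assessment schedule or attribution rule for the event.

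Table 5 ("Measures collected from patients at each of three survey timepoints") marks PROMIS depression and anxiety, the PSS and the PCS at T1, T2 and T3. Table 3 converts in-app answers into dashboard categories: a mood total of 12 or more shows Low Mood, and a catastrophizing total of 10 or more shows High Stress.

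The stated uses of these data are:
- trends (section 1.0);
- "potential mediators of intervention effects" and symptom trajectory (section 9.3, Survey assessments);
- an exploratory analysis in sections 8.1 and 11.2, where "we will explore associations between levels of engagement and changes in pain severity/interference, opioid use, catastrophizing, sleep, mood, and pain self-efficacy".

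**The concern.** The plan identifies one harm, makes it the only reportable adverse event, and measures it repeatedly with standard scales. The reporting rule and the measurements are not connected. A patient whose PROMIS depression, PROMIS anxiety or PSS score clearly worsens over the 4 weeks enters the report as an adverse event only if the treating clinician independently reaches that judgement. The public text schedules no study assessment by that clinician during the 6 weeks.

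Section 8.2 says the pilot is to inform the app and procedures of a later efficacy study. A report with no distress events, alongside group trends that look flat or favourable, could be carried into that study although some individuals deteriorated on the pilot's own scales. With about 10 analysed patients, one or two such individuals matter, and a mean can absorb them.

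**Working it through.** The plan gives no figure to reproduce on this point. The check is a reading of the text, followed by two illustrations with assumed inputs.

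**1. Does any section link a worsened score to the adverse event or to a count?**

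| Source of information | Where | What the plan does with it |
|---|---|---|
| Clinician's determination | Section 12 | Monitored and reported as the adverse event |
| PROMIS depression/anxiety, PSS | Table 5, T1–T3 | Mediators, trajectory, association with engagement |
| In-app mood and catastrophizing | Table 3 | Dashboard category, care-team prompt |
| Elevated symptoms | Section 12.2 | Research assistant shares them with the nurse navigator |
| Severe distress due to the study | Section 12 | Research assistant notifies the care team |

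Only the first row produces a reported event. No row produces a count of patients who deteriorated. Table 2, which triggers the secure message in section 9.3, has no depression, anxiety or distress item; the nearest is hallucinations/nightmares. Table 3 also triggers a message for responses in red, but the colours are lost in the text version, so it cannot be seen whether Low Mood or High Stress is among them.

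**2. How easily could no event be recorded?** Let p be the true share of patients distressed by the app and s the chance that the treating clinician records a true case. Both are assumptions. From section 9.3, n = 10 (core cohort) or 15 (all enrolled).

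P(no event recorded) = (1 − p·s)^n

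| n | p | s = 1 | s = 0.5 | s = 0.25 |
|---|---|---|---|---|
| 10 | 10% | 34.9% | 59.9% | 77.6% |
| 10 | 20% | 10.7% | 34.9% | 59.9% |
| 10 | 30% | 2.8% | 19.7% | 45.9% |
| 15 | 20% | 3.5% | 20.6% | 46.3% |

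For example, with n = 10, p = 0.2 and s = 0.5: (1 − 0.1)^10 = 0.349.

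Even with complete recording, zero events is weak evidence. The one-sided 95% upper limit is 1 − 0.05^(1/n), which is 25.9% for n = 10 and 18.1% for n = 15.

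**3. Can a group mean hide individual worsening?** Assume harmed patients worsen by 10 points on average, the others improve by 4, and the SD of change within each group is 5.

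- 2 of 10 harmed: mean = (8 × (−4) + 2 × 10)/10 = −1.2. The SE is 5/√10 = 1.58, so P(mean shows improvement) = Φ(1.2/1.58) = Φ(0.76) ≈ 78%.
- 3 of 10 harmed: mean = (7 × (−4) + 3 × 10)/10 = +0.2, so P(mean shows improvement) = Φ(−0.2/1.58) = Φ(−0.13) ≈ 45%.
- 2 harmed, one of them without a T2 score: mean = (8 × (−4) + 1 × 10)/9 = −2.4. Losing the harmed patient makes the mean look better.

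Masking by the mean is therefore possible and needs no assumption about engagement, but it is not certain. With 3 of 10 harmed, the mean shows improvement in slightly fewer than half of trials.

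**The case against.** **The care team does hear about distress.** Section 12.1 has symptom reports reviewed daily and shared with nurse navigators. Section 12.2 has elevated symptoms passed on for follow-up, and section 12 has severe distress notified. Section 9.3 adds weekday dashboard checks twice daily. Chart abstraction records anxiolytics and antidepressants started during the study and psychosocial visits, and the interviews cover study burden. All this stands, and it means distress is not ignored clinically. These routes serve care, however. The navigator is not the person who determines the event under section 12, and no section counts the notifications or the deteriorations. The sentence that "there is no expectation for proactive clinician outreach" concerns prompts for severe symptoms; it should not be read as a rule about how adverse events are determined.

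**Appendix N may supply what is missing.** It was not available, and its absence is not a fault of the plan. The point is limited to the protocol text, and the sponsor should check the appendix first.

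**A stronger reading is tempting.** A reader might infer that the scales are analysed only as benefit outcomes, or that the engagement analysis would turn harm into apparent benefit. The documents do not support either. Mediators, trends, trajectory and changes are direction-neutral terms, so worsening would appear as worsening. An engagement association would look favourable because of harm only if distressed patients used the app less. With equal engagement, harm would push it in neither direction, and section 9.4 ties the risk to daily reporting and content review, so heavier users could equally be the more distressed. Sections 8.1 and 11.2 also concede that power is insufficient for this exploration.

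**Counting deterioration in advanced cancer picks up noise and disease.** This is right as regards any worsening at all, which random drift alone would produce in about half of patients. It argues for a cut-off fixed in advance and a descriptive label; it does not argue for leaving the count out.

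**Conclusion.** The point holds in a limited form. In the public text, the single reportable adverse event depends on the treating clinician's judgement without a stated criterion, and no planned summary counts patients who deteriorate on PROMIS depression, PROMIS anxiety or PSS, or who move into an adverse in-app category. App-related distress, a risk the plan itself names, can therefore be under-recorded, and group means can conceal it.

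The size cannot be derived from the documents. With 10 patients and 20% distressed, the chance of recording no event runs from 10.7% to 59.9% as assumed clinician recording falls from complete to one in four. The masking example depends on the assumed changes and SD. Neither shows that under-recording will occur; both show that the plan as written would not reveal it.

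In a minimal-risk, single-arm feasibility pilot this is a cheap improvement to harm reporting and does not undermine the feasibility endpoint. It would fall away to the extent that Appendix N already specifies such a review and summary.

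**What to change.** First check whether Appendix N already covers this. If it does not, keep the clinician-determined event and every existing notification route unchanged, and add to sections 11.2 and 12 a descriptive safety table built from each patient's own change:

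- **Population:** all enrolled patients, including the first 5. Section 9.3 leaves them out of the final analysis although they follow the same procedures.
- **Scales:** number and percentage worsening beyond a cut-off that the sponsor fixes in advance, T1 to T2 and T1 to T3, on PROMIS depression, PROMIS anxiety and PSS.
- **In-app flags:** number moving into Low Mood or High Stress (Table 3) after their first report.
- **Early stoppers and missing T2:** listed separately with their last in-app category, which must not stand in for a PROMIS or PSS score.
- **Interpretation:** a sentence that the exploratory engagement–mood association is not evidence that distress is absent.

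The cost is a few sentences and one table, with no new data, visits or staff. The downside is that, without a control group, some worsening will reflect the cancer, and repeated in-app reports will catch transient changes. The table must therefore be labelled descriptive and not attributed to the app. The cut-off is a reporting threshold only and sets no clinical action.
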